### **12.3 Baseline assessment**

Baseline tests and procedures must be performed and reviewed before allocation. The following information/assessments will be collected at the baseline visit:

1. Inclusion/exclusion criteria review
2. Collection of baseline information (Appendix 4)

3. Collection of primary and secondary outcomes
4. Randomization

### **12.4 Study completion**

The end-of-study is defined as the date of the last participant's last scheduled assessment, 12 months after enrollment.

### **12.5 Collection of data from hospital records**

All relevant information on participants will be collected using online Case Report Forms (CRF). No additional information will be collected from the included participant's hospital records.

## **13.0 DETERMINATION OF SAMPLE SIZE AND STATISTICAL ANALYSIS PLAN**

### **13.1 Determination of Sample Size**

The study will be powered to detect a difference in change of 9 points between the two groups in the primary outcome (LEFS) from baseline to 6 months follow-up. The 9 point change has previously been recommended and applied in similar studies as the minimal clinically important difference in LEFS. To detect this difference, we will need 94 patients in each group (assuming a common SD of 19, power = 90%, alpha level = 0.05). We plan to recruit 226 patients to account for loss to follow-up (20%).

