## **8.0 SELECTION AND ALLOCATION OF PARTICIPANTS**

### **8.1 Number of participants planned**

It is anticipated that 226 participants will be enrolled in this study. A participant may be enrolled in this study provided he/she has met all the inclusion criteria and has not met any of the exclusion criteria.

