## **8.4 Allocation of participants and sequence generation**

We will stratify the randomization by

- Site (2 levels; Slagelse Hospital and The Regional Hospital in Horsens)

The allocation ratio will be 1:1.

Randomization lists will be computer-generated based upon permuted random blocks of variable size (3 to 6 in each block).

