### **13.5 General statistical approach**

For quantitative variables we will calculate mean, standard deviation, median, range and number of missing data.

All summary tables for qualitative variables will display counts, percentages and number of missing data (if relevant) by treatment group.

All statistical tests will be two-sided and statistical significance will be claimed if the computed p-value is equal to or less than 0.05.

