## **13.6 Primary analysis**

### **13.6.1 Primary outcome analysis**

The primary endpoint is the change from baseline in the lower extremity functional scale at the 4-week follow-up. The primary analysis will be done on the ITT population.

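### The recruitment target of 226 covers a loss of 16.8%, not the stated 20%; at 20% loss the power is about 89% rather than 90%

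*Combined protocol and SAP*

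**What the plan says.** Section 13.1 sets the target difference: "The study will be powered to detect a difference in change of 9 points between the two groups". Its other inputs are "assuming a common SD of 19, power = 90%, alpha level = 0.05", and its result is "we will need 94 patients in each group". The allowance for attrition follows: "We plan to recruit 226 patients to account for loss to follow-up (20"%). No inflation formula is given.

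Section 8.1 repeats the total: "It is anticipated that 226 participants will be enrolled in this study". Section 7.1 gives the same number in words. Two further inputs come from elsewhere. Section 13.5 states "All statistical tests will be two-sided", and section 8.4 states "The allocation ratio will be 1:1". For the primary analysis, section 13.6.1 says "The primary analysis will be done on the ITT population" and names no method for missing outcomes.

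**The concern.** A sample size that accounts for 20% loss should still leave the required number after 20% of those recruited have gone. Here the required number is 188, and 80% of 226 is below it. The total appears to come from adding 20% to the number needed at the end, when the number needed should have been divided by the fraction expected to remain.

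What is at stake is the accuracy of the plan's main design figures. Recruitment, tolerated loss and power are stated as a set, and readers will judge the trial's precision by them. As written, the set is inconsistent, and a single division shows it.

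**Working it through.** **Inputs.** From section 13.1: difference δ = 9 points, SD σ = 19, power 90%, α = 0.05, 94 per group, loss 20%, total 226. From section 13.5: two-sided tests. From section 8.4: equal allocation.

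**1. Reproduce the 94 per group.** By the normal approximation,

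n = 2 × [σ (z₀.₉₇₅ + z₀.₉₀) / δ]² = 2 × [19 × (1.960 + 1.282) / 9]² = 93.66, rounded up to 94.

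This matches the plan, so the base of 2 × 94 = 188 is not in dispute. A one-sided test would need only 77. The t-test version gives 94.63, that is 95.

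**2. Reproduce the 226.**

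- Multiplying: 188 × (1 + 0.20) = 225.6, rounded up to 226. This is the stated total.
- Dividing: 188 / (1 − 0.20) = 235, or 236 (118 per group) for equal arms. This is not the stated total.

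The gap is 235 − 226 = 9 recruits, too large to be rounding.

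**3. What 226 leaves after 20% loss.**

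- 226 × 0.80 = 180.8, or 90.4 per group.
- Shortfall against 188: 188 − 180.8 = 7.2 analysable participants.
- Largest loss that still leaves 188: 1 − 188/226 = 38/226 = 16.8%.

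**4. Power.** By the normal approximation, power = Φ(δ / (σ √(2/n)) − 1.960). At n = 90.4, this is Φ(9 / (19 × 0.1487) − 1.960) = Φ(1.225) = 0.890.

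| Analysable per group | Situation | Normal approximation | t-test |
|---|---|---|---|
| 113 | 226 recruited, no loss | 94.5% | 94.4% |
| 94 | Number required by section 13.1 | 90.1% | 89.8% |
| 90.4 | 226 recruited, 20% lost | 89.0% | 88.6% |

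**5. Detectable difference at 90% power.** By the normal approximation, δ = σ (z₀.₉₇₅ + z₀.₉₀) √(2/n). At 90.4 per group this is 19 × 3.242 × 0.1487 = 9.16 points, against 8.98 at 94 per group. By the t-test the values are 9.21 and 9.03. Under either method the change is about 0.18 points on the 80-point scale.

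**The case against.** The strongest objection is materiality. The loss of power is a little over one percentage point. By the t-test, the plan's own 94 per group already gives 89.8%, so part of the gap between 88.6% and 90% comes from the choice of approximation. That is fair, and it limits the weight of the point. It does not make the stated figures consistent, because under either method 20% loss costs about 1.2 points relative to 94 per group.

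A second objection is that 181 is a complete-case count. The primary analysis uses all randomized participants, and section 13.3.3 defines a separate as-observed population without imputation, which suggests that the ITT analysis is not meant to be complete-case. LEFS is also collected at weeks 1 to 3, so a repeated-measures model or imputation could recover some information. This stands as a condition on the result. However, the plan specifies no such method, so any recovery cannot be counted or quantified. The plan's own allowance for loss also treats lost participants as not contributing.

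A third is that section 13.1 refers to change to 6 months while the primary endpoint is at 4 weeks, so it is unclear to which time point the 20% and the SD of 19 belong. That is a separate inconsistency that also needs settling. The inflation arithmetic is the same at either time point.

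Finally, 226 would be right if the 20% meant a share of the 188 completers. Nothing in the documents gives it that unusual meaning.

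**Conclusion.** The concern holds. The total of 226 comes from multiplying by 1.20 where dividing by 0.80 was needed. At the stated loss it leaves about 181 analysable participants where 188 are required, and power of 89.0% (normal approximation) or 88.6% (t-test) where 90% is stated. It meets the plan's own requirement only if loss is no more than 16.8%.

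The error is small. It is no reason to regard the trial as materially underpowered, and with full follow-up 226 would give more than 94% power. The result takes the 9 points and SD of 19 as given and counts lost participants as contributing nothing to the primary comparison.

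**What to change.** Keep 226 and correct the statement in section 13.1, for example: 226 participants allow for a loss of 16.8% at 90% power; with 20% loss, about 181 participants would provide the primary outcome, and the power to detect 9 points (SD 19, two-sided α 0.05) would be about 89%. Name the time point to which the loss and the SD apply, in line with however the 4-week and 6-month references are reconciled.

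The cost is one sentence and a slightly less favourable figure. Conduct, enrolment and analysis do not change. If the sponsor prefers to keep 90% power at 20% loss, the target becomes 235 (236 for equal arms), which is 9 or 10 more participants, and sections 7.1, 8.1 and 13.1 would all need the new number. The gain of about one percentage point of power does not require this.

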### **13.2 Participants description**

#### **13.2.1 Disposition of Participants**

The total number of randomized participants will be summarized by site using counts and percentages. The number of patients either completing or discontinuing the study will be summarized using counts and percentages.

### **13.3 Study Population definitions**

#### **13.3.1 Intention to treat population (ITT)**

The ITT population consists of all randomized patients regardless of whether the patient received study intervention or failed to comply with the study protocol, in the treatment group to which the participant was assigned (see Figure 2).

#### **13.3.2 Per protocol (PP)**

The per protocol population consists of participants in the ITT population with a valid baseline measurement of the variable to be analyzed.

#### **13.3.3 As-observed population (AO)**

The AO population consists of participants who has the outcome of interest assessed at a given time point of interest (i.e. no imputation of missing data will be done).

### **13.4 Data analysis considerations**

The primary outcome is change from baseline in the lower extremity functional scale and will be analyzed using the ITT population.

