## **10.0 OUTCOME ASSESSMENTS/VARIABLES**

### **10.1 Primary Outcome**

#### **10.1.1 Lower extremity functional scale**

The primary outcome measure is the change from baseline in the Lower extremity functional scale (LEFS) assessed at 4 weeks after randomization. LEFS will also be assessed at 1, 2 and 3 weeks, and 3, 6 and 12 months, these timepoints will be regarded as secondary outcomes.

The Lower extremity functional scale is a self-completed questionnaire providing a total score based on the patients subjective ankle function. The scale consists of 20 functional leg activities, each scored on a five point scale (0 impossible, 4 no difficulty), giving a minimum score of 0 (worst) to 80 (best). The questionnaire will be translated into Danish using a dual-panel approach before trial start. The LEFS will be scored online by the trial participant. This approach avoids the requirement for follow-up visits in a clinic.

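### The primary week-4 LEFS analysis does not use baseline LEFS or site; adjusting for both would gain precision at no data cost

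*Combined protocol and SAP*

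**What the plan says.** Section 13.6.1: "The primary endpoint is the change from baseline in the lower extremity functional scale at the 4-week follow-up". Section 13.4 ties this to the ITT set: "The primary outcome is change from baseline in the lower extremity functional scale and will be analyzed using the ITT population". Section 13.3.1 defines that set as follows: "The ITT population consists of all randomized patients regardless of whether the patient received study intervention or failed to comply with the study protocol". Section 13.5 lists descriptive statistics and adds: "All statistical tests will be two-sided and statistical significance will be claimed if the computed p-value is equal to or less than 0.05". No section names a test, a model, an effect estimate with a confidence interval, or a covariate.

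Two items that could serve as covariates are already in hand. LEFS is collected at baseline as a primary outcome (12.3), and randomization is stratified by "Site (2 levels; Slagelse Hospital and The Regional Hospital in Horsens" (8.4). Repeated scores are also planned: "LEFS will also be assessed at 1, 2 and 3 weeks, and 3, 6 and 12 months" (10.1.1).

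The only statement on missing values, "no imputation of missing data will be done", belongs to the as-observed set in 13.3.3. Nothing says how a randomized participant without a week-4 score enters the ITT analysis.

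**The concern.** The sample size in 13.1 is that of a plain two-group comparison of change, and nothing in section 13 goes beyond it. A change score fixes the weight on baseline at 1. Regression on baseline estimates that weight, which removes variance unless 1 happens to be the best value. The plan also stratifies by site but gives the stratum no place in the analysis. What is at stake is precision that the trial has already paid for: the width of the confidence interval for the week-4 difference, and power.

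There is a second, smaller issue. An analysis of all randomized participants cannot be carried out until there is a rule for those lacking the scores it needs. Section 13.3.2 defines the per-protocol set by a valid baseline value, so the plan itself allows for ITT members without one.

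**Working it through.** **Inputs.** From 13.1: a 9-point difference, SD 19, 90% power, alpha 0.05, 94 per group, 226 in total, 20% loss. From 13.5: two-sided tests. Section 13.1 refers to a "difference in change of 9 points between the two groups in the primary outcome (LEFS) from baseline to 6 months follow-up", so using its SD and loss at week 4 is an assumption. Whether 19 is the SD of change or of a single score is not stated. Also assumed: r, the baseline-to-week-4 correlation, at 0.2, 0.5 and 0.8; and k, the week-4 SD divided by the baseline SD, at 1 and 1.5. The site term is left out of the calculation.

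**The plan's own figure.** 2 × (19/9)² × (1.960 + 1.282)² = 93.7, which rounds up to 94 per group. This reproduces. With 226 randomized and 20% lost, 226 × 0.8 / 2 = 90.4 per arm remain.

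**Precision.** Write s for the baseline SD.
- Variance of change = s²(1 + k² − 2rk).
- Residual variance after adjusting for baseline = s²k²(1 − r²).
- The first minus the second = s²(1 − rk)². This is never negative and is zero only when rk = 1.
- Ratio of adjusted to change variance = k²(1 − r²)/(1 + k² − 2rk), which is (1 + r)/2 when k = 1.

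Results for a two-sample t test of 9 points, with 19 as the SD of change, 90.4 per arm, and one degree of freedom fewer after adjustment:

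| Analysis | r | Variance ratio | Power | 95% CI half-width |
|---|---|---|---|---|
| Change score | any | 1 | 88.6% | 5.58 |
| Adjusted, k = 1 | 0.2 | 0.60 | 98.3% | 4.32 |
| Adjusted, k = 1 | 0.5 | 0.75 | 95.5% | 4.83 |
| Adjusted, k = 1 | 0.8 | 0.90 | 91.6% | 5.29 |
| Adjusted, k = 1.5 | 0.2 | 0.82 | 93.9% | 5.04 |
| Adjusted, k = 1.5 | 0.5 | 0.96 | 89.7% | 5.48 |
| Adjusted, k = 1.5 | 0.8 | 0.95 | 90.1% | 5.44 |

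At 10% loss (101.7 per arm) with k = 1, power goes from 91.9% to 99.1%, 97.3% and 94.3% at the three values of r.

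If 19 is instead the SD of a single score (k = 1, 20% loss), change-score against adjusted power is 70.7% against 89.8% at r = 0.2, 88.6% against 95.5% at r = 0.5, and 99.9% against 99.95% at r = 0.8.

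**Endpoint.** With baseline in the model, replacing the week-4 score by change only moves the baseline coefficient by 1. The treatment estimate is identical.

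**Non-response.** This was simulated with 113 per arm, baseline correlated 0.5 with weeks 3 and 4, and weeks 3 and 4 correlated 0.8. In one arm only, the log-odds of a missing week-4 score change by 1 per SD of week-3 LEFS. Approximate bias:

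| Analysis | 10% loss | 20% loss |
|---|---|---|
| Change score, responders | 0.5 | 1.0 |
| Week-4 ANCOVA, responders | 1.0 | 1.8 |
| Weeks 3–4 likelihood model, week 3 complete | under 0.1 | under 0.1 |
| Same, half of week-4 non-responders also miss week 3 | – | 0.8 to 0.9 |
| Same, all of them also miss week 3 | – | 1.8 |

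At 20% loss with no true difference, rejection rates are 5.4–6.8% for the change score, 10.3–11.3% for ANCOVA, and 4.6–5.0% for the likelihood model with week 3 complete. If non-response is random, or depends on week 3 alike in both arms, no method is biased. Under random loss of 20% the weekly data then add about 1 point of power (97.3% against 96.1%).

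**The case against.** The strongest case against is that this is missing detail rather than an error. The endpoint, time point, population and alpha are all fixed, 94 per group reproduces, and the documents give none of the quantities that set the size of the gain. All of that stands. The gain runs from nil to about 19 points of power, depending on assumptions that the plan does not settle.

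Three stronger readings are tempting, and none is supported.
- A reader might infer that the plan commits to an unadjusted test, or to responders only. It does not: it names no test, and the no-imputation phrase applies only to the as-observed set.
- A reader might infer that baseline adjustment or a weekly mixed model would cure non-response bias. In the one-arm scenario, week-4 ANCOVA on responders is further off than the responder change score. The likelihood model is near zero only if those who miss week 4 answered week 3, which the documents do not establish. The simulation also used weeks 3 and 4 only; a weeks 1–4 model was not tested.
- A reader might infer that a mixed model automatically includes everyone randomized. With baseline as a covariate it drops participants without a baseline LEFS, and those with no weekly score.

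Baseline timing can also be raised: 10.3 and 12.2 place it after randomization, 12.3 before allocation. That needs reconciling, but it does not favour the change score. A baseline shift of d in one arm biases the change score by d and the adjusted estimate by the regression slope times d, which is smaller whenever the slope is below 1.

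**Conclusion.** The point holds as one of precision and should be fixed. The plan leaves baseline LEFS and site out of its primary analysis, and using them costs no data. The direction of the gain is secure in large samples. Its size is not: with 90.4 per arm and 19 as the SD of change, it is about 3 to 10 points of power at equal SDs (r from 0.8 to 0.2), about 1 to 5 points if the week-4 SD is 1.5 times baseline, and nothing when rk = 1. These figures borrow the SD and loss from a 6-month calculation and assume r and k. No number stated in the plan is wrong because of this gap. The missing rule for absent scores is a real omission, but the documents do not show which way, or how far, it would move the result.

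**What to change.** In 13.6.1, state: *The primary estimate is the between-group difference in LEFS at week 4 with 95% CI, adjusted for baseline LEFS and site, with participants analysed as allocated.* The endpoint and the 9-point target are unchanged.

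One suitable way to fit it is a mixed model of LEFS at weeks 1 to 4 with treatment, week, treatment-by-week, baseline, baseline-by-week and site, and an unstructured covariance, reporting the week-4 contrast. Participants who miss week 4 but answered earlier then contribute. Other pre-stated baseline- and site-adjusted analyses are acceptable. If week-4 ANCOVA is chosen, describe it as a precision adjustment and state a separate missing-data method.

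State how participants with no baseline LEFS, and those with no post-baseline LEFS, are kept in the ITT analysis, for example by a constrained-baseline model or multiple imputation. A sensitivity analysis that shifts unobserved week-4 values in one arm over a stated range is optional.

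The cost is wording only: no added participants, visits or forms. The statements on baseline timing in 10.3 and 12.2 must be reconciled with 12.3 as a separate item.

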### **13.5 General statistical approach**

For quantitative variables we will calculate mean, standard deviation, median, range and number of missing data.

All summary tables for qualitative variables will display counts, percentages and number of missing data (if relevant) by treatment group.

All statistical tests will be two-sided and statistical significance will be claimed if the computed p-value is equal to or less than 0.05.

#### **13.5.1 Concomitant medication and/or therapy**

The use of concomitant medications and/or therapies (e.g. GP consultations, physiotherapy, etc.) will be summarized in each treatment group.

## **13.6 Primary analysis**

### **13.6.1 Primary outcome analysis**

The primary endpoint is the change from baseline in the lower extremity functional scale at the 4-week follow-up. The primary analysis will be done on the ITT population.

### **13.6.2 Data transformation before analysis, if any**

No data transformation will be applied to raw data.

## **14.0 STUDY COMMITTEES**

### **14.1 Protocol Development Committee**

#### **14.1.1 Membership**

The Protocol Development Committee of this study is composed of scientific, technical, and administrative persons from participating sites and other collaborating participants. There are no restrictions to the number of members in the committee.

#### **14.1.2 Roles and responsibilities**

This committee, led by its chairman [name], is responsible for development, refinement, and finalization of this protocol and planning of activities related to the study.

This study was conceptualized by [name] (Study Chairman and principal investigator). The initial version of the protocol (version 1.0) was developed by [name].

## **15.0 ETHICS**

### **15.1 General considerations**

Prior to assessment for eligibility the trial participants will be informed, both orally and in writing, about the purpose of this trial, the overall duration and potential risks, as well as costs and benefits for participation. The leaflet “*Forsøgspersoners rettigheder i et sundhedsvidenskabeligt forskningsprojekt*” will be handed out and participants will be encouraged to read it before trial enrolment. All participants are informed of their rights to withdraw from the study. The participant may withdraw oral, written or with other clear indications about the attend to resign from the research project. If the participant withdraws their consent, this will not affect their right to present or future treatment or any other rights they may have. After the information is delivered, read and understood, voluntary informed consent is given by the participant by signing a consent form before trial participation can take place.

### **15.2 Oral information**

When a potential participant is identified during initial assessment in the ED he/she will be given information about this trial. If further investigations are needed to determine eligibility for enrollment, the information will be given after completion of these. It will be stressed that the investigator is asking the participant to consider participation in the trial, and that the potential

trial participant has the right to bring a companion to the information interview, if possible. The written information material will be handed out in the ED by the trial investigator. The participants will not be able to have a 24-hour consideration period before inclusion in the study, but will have sufficient time to consider inclusion. The oral information will be given in a language easily understood without technical or value-laden terms. The information will be given in a considerate way that is tailored to each potential trial participants. The conversation will take place without interference. It is the responsibility of the interviewer to ensure that the potential trial participant has understood all the information giving. Guidelines for the oral information are given in Appendix 6.

